## 5.11 Dissemination of results

[figure not shown]
At the end of the study, the principal investigator will submit a report on the study and its main outcomes. This report will be shared with the national malaria control programme and the Ministry of Health and will enable recommendations to be formulated and the Ministry of Health to make informed decisions about whether the current guidelines should be updated. The data will also be shared with the WHO Global Malaria Programme so that they can be included in the Malaria Threats Map (36) and the World Malaria Report. The study report should:

- indicate if the study will be presented during a scientific meeting or published;
- indicate how the results will be disseminated to the study patients; and
- if the study is community-based, mention how the community will be informed and how community participation will be maintained.

## 6. Study timeline

It should be noted that the amount of time it will take to enrol the desired number of survey participants will depend on: (i) the number of suspected malaria cases seen each week at each facility; (ii) the test positivity rate (i.e. the number of positives per suspected malaria case) at each facility; and (iii) the sample size needed to detect whether the observed prevalence of false-negative HRP2 RDT results caused by *pfhrp2/3* gene deletions is above the 5% threshold (see section 5.4). Prior to implementing this protocol, the national malaria control programme and surveillance teams should assess the expected time needed to enrol the desired number of respondents within each domain and plan accordingly. An example timeline is presented in Table 6; note that the start month will depend on the local transmission context.

**Table 6. Illustrative survey timeline**

## 7. Human subjects

### 7.1 Overview

All investigators will be trained in the ethical conduct of human research, the study objectives, methods of effective communication with study participants, and collection of high-quality data. The importance of informed consent and how to administer consent forms should be emphasized, and the study team will receive additional training specific to the tasks they will perform (e.g. interview techniques, sample collection and data confidentiality).

Prior to fieldwork being conducted, the relevant ethics committees/institutional review boards will be presented with all of the necessary documentation, including report forms, proposed procedures to minimize risk in the process of data collection, and consent forms and data management plans to ensure the confidentiality and safety of data.

All research participants will be asked to provide individual consent (or assent depending on the age of majority and federal guidelines in the country of enrolment) for their participation. Consent for long-term storage/biobanking is separate from consent to participate in the survey. In all cases, consent is voluntary, and participants have the right to refuse or withdraw at any time.

Informed consent will be obtained both verbally and in writing from all participants in the preferred local language (Annex 4). As part of the consent process, the survey and biobanking will be explained and the consent form will be read to each person or given to participants to read themselves. Participants will be asked questions to ensure their comprehension. It will be emphasized that participation is voluntary, and that participants have the right to withdraw consent at any time and the right to refuse to answer any questions. The consent form will detail the design of the survey and the biobanking and analyses to be done, including a description of data storage.

If participants agree, they will be asked to sign the consent or assent form, or, if illiterate, provide a thumbprint in conjunction with the signature of an independent witness, depending on national guidelines.

For children under the legal age, consent will be obtained from at least one parent or guardian; this is sufficient given the minimal risk posed. In addition, assent (Annex 5) will be obtained from children, depending on the age of majority and federal guidelines in the country of enrolment, in addition to the consent of a parent or guardian. Children providing assent will be asked to sign next to their name or provide a thumbprint accompanied by the signature of an independent witness on the assent form. In cases where subjects under 18 years of age are considered “mature minors” (sometimes defined as pregnant, married or otherwise the head of their household, depending on the country-specific context) and are able to provide consent for themselves, assent will not be sought. Examples of consent and assent forms are included in Annexes 4 and 5. The reading level of the consent form should be no higher than primary school level 8. All interviewers will be trained extensively in the consent procedure, and each form will be co-signed (or verified by their mark) by a team member to ensure that all participants have consented. A copy of the consent information sheet will be given to each subject and the certificate of consent maintained by the survey team. The names of the investigators will be included on all consent forms, with phone numbers and addresses for the participants to use if they have any questions or if they wish to withdraw their samples from the biobank in the future.

## 7.2 Risks to human subjects

This survey and biobanking activity is of minimal risk to participants. The amount of blood collected is very small (~100–200  $\mu$ L), and participants may experience only a small bruise at the site from which blood is collected. The initial prick may lead to minor temporary discomfort or pain.

Trained personnel will perform finger pricks to ensure that they are done in as safe a manner as possible. Precautions will be taken to avoid bleeding by applying cotton wool and pressure immediately to the prick site. Risk of infection will be minimized by cleaning the finger with an alcohol swab prior to pricking and using disposable lancets – one for each individual to avoid cross-contamination/transmission of infectious agents. Any concerns about potential risks will be mitigated as much as possible, e.g. through community sensitization prior to the survey.

## 7.3 Protection against risk

The survey and biobanking data collected are not considered to be of a sensitive nature. Therefore, there are minimal risks expected for the participant. Concerning confidentiality, only consenting patients will write their name on the consent form, but this will not appear in any other registries/tally sheets, forms or diagnostic specimens associated with the survey or biobanking process. Steps will be taken to ensure that each study participant's name is protected. There is no linkage between clinic registries (which contain personal information) and survey report forms. DBS/filter paper samples and other samples will be labelled using a survey ID only and consent for biobanking will be indicated directly on the DBS.

The proposed strategy to reduce any risks includes the following:

1. Explain the physical procedures carefully to each participant so that they understand the potential pain associated with the collection of malaria data but that the pain is most likely to be temporary.

2. Ensure that health workers can answer commonly asked questions and understand the nature of the questions being asked.
3. Ensure that health workers using RDTs in their routine work are observed for their competency in collecting and handling biological specimens and that all data entry personnel (these may also be the health workers) are trained in confidentiality, safety and informed consent procedures. All team members should be trained in universal precautions for handling biological specimens.
4. Train field supervisors in protocol management. Spot checks by the supervisory staff will provide further assessment of protocol management.
5. Use the most efficacious testing procedures available to ensure sterile and safe biological data collection and testing. The blood for RDTs/microscopy and DBSs will be collected simultaneously.
6. Assess the practices for protecting against any blood-borne infections, including HIV, according to national guidelines, and corrective action plans should such infection occur from needle sticks during the collection of data. Training/ re-training in the standard universal precautions (i.e. use of gloves and sterile equipment for all fluid transactions) will minimize the possibilities of transmission from participants to data collectors or vice versa. If a needle stick should occur, the recipient will immediately be offered appropriate counselling and treatment from the nearest relevant health facility according to the national protocol.
7. Ensure that the confidentiality procedures are designed to meet all contingencies in order to preserve the privacy of the participants.

## 7.4 Data monitoring and protection plan

Participants, parents and guardians will be informed that participating in a research study may involve a loss of privacy. All records will be kept as confidential as possible, and steps will be taken to ensure that each survey/biobanking participant's personal information is protected. All long-term storage of personal data will be labelled with the participant's survey ID. Filter paper samples will be labelled using only a unique survey participant ID number, or barcode, which will only be linkable through the consent form (for consenting individuals), initially by the enrolling clinician and then later by the study coordinator and principal investigator. For the laboratory analyses, there will be no link between the laboratory samples and the participant's identifiable information. All consent forms with survey IDs will be stored in locked cupboards and on password-protected computers accessible only by the study coordinator and the principal investigator. No individual identities will be used in any reports or publications resulting from the study.

## 7.5 Incentives

There will be no money or commodities offered as incentive for participation in the survey or biobanking.

## Annex 1. Supplemental data analysis to determine the prevalence of *pfhrp2/3* gene deletions

To achieve the survey protocol primary output measures, only samples from patients with suspected *pfhrp2* deletions are prioritized for analysis for *pfhrp2/3* gene deletions. This approach reduces the number of patient samples that need to be transported and analysed by PCR and/or serology. However, as outlined in Table A1.1, there are limitations to this approach, as other malaria suspects with *pfhrp2/3* gene deletions will be missed. If after assessing the resources available to analyse the suspected *pfhrp2/3* deletions, there are funds available, additional analysis can be conducted on a subset of DBSs from HRP2 RDT positive and negative patients (missed by both RDTs or by RDT and microscopy). The former will identify infections caused by *pfhrp2*-negative but *pfhrp3*-positive parasites that still react with HRP2-based RDTs due to cross-reactivity between HRP2 and HRP3, as well as multiclonal infections with parasites with and without *pfhrp2/3* deletions. The latter will determine the presence of *pfhrp2/3* deletions in very low-density infections.

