## 5.6 Data collection and fieldwork

The following general steps for data collection will be followed. **(Note that it will be necessary for each country to develop a specific standard operating procedure in order to tailor these steps to its particular context and needs.)**

The national malaria programme should identify the domains to be surveyed. A sampling domain can be a province, district, state or other unit, depending on the administrative boundaries of the country. This selection should be guided by an assessment of which domains may be most at risk for *pfhrp2/3* gene deletions; otherwise, domains can be randomly selected based on epidemiological zones. Domains with low, moderate and high transmission should be considered, whereas domains without malaria transmission should be omitted. The sample sizes may be reached more quickly in moderate to high transmission areas; however, the expected higher prevalence of multiclonal infections may mask the presence of *pfhrp2/3*-deleted parasites. This issue is less likely in low transmission areas and therefore these zones should be included.

1. Select a specified number of public health facilities (aiming for 10) in each domain of the country routinely using malaria RDTs to be included in the survey.
  - The number of facilities per domain to be included in the sample should take into account the expected mean number of suspected *P. falciparum* cases seen in the facility each week and the mean test positivity rate in the target area in order to ascertain the expected number of positive cases each week. As a general rule, the aim is to finish the fieldwork and collect a minimum sample size of 300 positive cases within an eight-week period (assuming 10 health facilities are selected; if the number of health facilities is reduced, a higher sample size will be required, as explained in section 5.4).
  - Health facilities for the sample should be selected from a complete list (sampling frame) of health facilities in each domain, using systematic random sampling based on probability proportional to size (28) (and proportional to the size of the facility type strata in each domain). The sampling frame must include some estimate of facility size (fever or suspected malaria case load) and type (e.g. public, private, level, etc.).

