#### 5.9.2.3 Characterization of *pfhrp2* and *pfhrp3* sequences and gene deletions in samples

Suggested primer sequences, PCR conditions and expected amplification product sizes for conventional PCR have been published by Cheng *et al.* (4). One of the limitations of this method is that it is a qualitative method and does not detect gene deletions when *pfhrp2*-deleted parasites are mixed with wild-type parasites in the same sample (especially when it is not the predominant strain). A recent review on methods related to *pfhrp2* deletion surveillance discussed the availability of several new molecular methods and their advantages and limitations (see Table 5 below), including various control requirements for reliable identification of gene deletions (35). Among these new methods, multiplex real-time PCR (22–24) and digital droplet PCR (27) are relevant for obtaining quantitative data and identifying deletions within mixed infections. Ideally, *pfhrp2* and *pfhrp3* genes should be characterized by amplification of two gene segments, namely exon 1 (including the intervening sequences between two exons) and exon 2 (including the intronic region between them). However, there are variations in the methods targeting different parts of the genes. Exon 1 codes for a signal peptide and exon 2 codes for the histidine-alanine-rich repeat region of each protein. PCR assays should include appropriate controls, including DNA from laboratory strains with known deletions, such as DD2 (*pfhrp2*-deleted) and HB3 (*pfhrp3*-deleted). If the *pfhrp2* and/or *pfhrp3* genes cannot be amplified despite good quality of DNA (see section 5.9.2.1), demonstrated by the amplification of other single-copy gene sequences, it suggests that the genes have been deleted. Optionally, in order to further confirm and characterize subtelomeric deletions, the following upstream and downstream flanking genes of

*pfhrp2* and/or *pfhrp3* can be amplified: the HPC230 gene located ~5.5 kb upstream and HSP70 located ~6.5 kb downstream of *pfhrp2*, and the HPC475 gene located ~1.7 kb upstream and ACL located ~4.4 kb downstream of *pfhrp3*.

Optional extra: If the *pfhrp2* gene can be amplified, the sequence of the exon 2 amplicon can be determined and translated into an amino-acid sequence. This will enable the classification of the HRP2 protein as type A, type B or type C/borderline structural group, according to the multiplied number of type 2 and type 7 repeats.

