**Table 5. Different PCR assays for detecting *pfhrp2* and *pfhrp3* genes with advantages and limitations (adapted from (35))**

Advantages	Limitations
Conventional PCR	

 
• Can be performed in most molecular laboratories and is widely used in many countries
 
• Can detect deletions of both exons
 
• Can identify deletions of flanking genes
 
	
 
• Time consuming at > 2 hours per reaction and qualitative method requiring visualization of PCR products on agarose gels
 
• Requires multiple different PCR reactions; > 6 reactions per sample for control and pfhrp2/3 genes and high volume of DNA needed
 
• Nested PCR and higher chances of contamination
 
• Cannot detect gene deletions when gene-deleted and non-deleted parasites are mixed in the same sample
 

Multiplex real-time PCR	

 
• Streamlined workflow with short turnaround time
 
• Quantitative read-out
 
• Can detect mixed infections with gene-deleted and non-deleted strains
 
• Different target genes are multiplexed in a single reaction, requiring less volume of DNA
 
	
 
• Requires multichannel real-time PCR machine
 
• Training is required for proper interpretation of results
 
• Careful optimization required for individual laboratories
 
• May not detect some partial gene deletions involving one exon, as most assays target one exon only
 

Digital droplet PCR	

 
• Higher confidence deletion calls than with other molecular methods
 
• Can clearly detect mixed infections with gene-deleted and non-deleted strains
 
	
 
• Requires specialized equipment that is not widely available
 
• Requires advanced laboratory and analysis expertise and training
 
• More expensive than conventional approaches
 

Sequencing approaches	

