### 1.3 Secondary output indicators (optional)

[figure not shown]
1. parasite density, as measured by quantitative PCR and/or microscopy, in patients with false-negative HRP2 immunoassay results (surrogates for HRP2 RDT negatives);
2. improved understanding of *pfhrp2/3* gene deletions, e.g. genetic relatedness and/or drug resistance and fitness, and new and/or improved diagnostic tools for detecting *pfhrp2/3*-deleted parasites; and
3. prevalence of parasites with *pfhrp2/3* deletions among all symptomatic *P. falciparum* confirmed cases.

The true prevalence of *pfhrp2/3* deletions can be determined only if all specimens included in the surveys are tested using molecular methods. When only HRP2-signal-negative specimens and a subset of HRP2-positive specimens are chosen for molecular analysis, the true prevalence of *pfhrp2* deletions is likely to be underestimated. This is because cross-reactivity between HRP2 and HRP3 will prevent some specimens lacking the *pfhrp2* gene from being selected for testing if only HRP2/3-negative specimens are chosen for molecular analysis.

The rest of the details for data analysis need to be followed as explained in the original protocol. The flow chart below (Fig. A2.1) summarizes important steps for using this alternative immunoassay-based screening to calculate (i) proportion of *P. falciparum* cases with suspected *pfhrp2/3* deletions and (ii) proportion of *P. falciparum* cases with false-negative HRP2 RDT results due to *pfhrp2/3* deletions.

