## 3. Molecular assays

Prioritize all HRP2/3-negative samples and samples with low HRP2/3 levels compared to other biomarkers (potential *pfhrp2*-deleted but *pfhrp3*-positive samples) and a subset of HRP2-positive and Pf-LDH-positive samples for molecular experiments to confirm deletion patterns of *pfhrp2* and *pfhrp3* genes. Although it is not a requirement, if resources are available, then all *P. falciparum*-positive samples can be tested for *pfhrp2/3* deletions. This will enable determination of the true prevalence of *pfhrp2/3* deletions in the sampling domain.

Different choices of molecular assays and relevant details are provided in the master protocol (section 5.9), and users can follow these guidelines.

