**REFERENCE LABORATORY USE ONLY**

17a.	Molecular analysis (Indicate the method chosen and make sure all the assay controls and analysis procedures are correctly followed)	
 
a. single copy gene 1 – present/absent/not done
 
b. single copy gene 2 – present/absent/not done
 
c. single copy gene 3 – present/absent/not done
 
d. HRP2 exon 1 – present/absent/not done
 
e. HRP2 exon 2 – present/absent/not done
 
f. HRP2 flanking 230 – present/absent/not done
 
g. HRP2 flanking 228 – present/absent/not done
 
h. HRP3 exon 1 present/absent/not done
 

17b.	Molecular method used	
 
a. Conventional PCR
 
b. Multiplex PCR
 
c. Digital PCR
 

18a.	Serology (indicate the method chosen and relevant controls used)	
 
a. pfhrp2+/pan-LDH+
 
b. pfhrp2-/pan-LDH-
 
c. pfhrp2+/pan-LDH-
 
d. pfhrp2-/pan-LDH+
 

18b.	Method of serological analysis	
 
a. Bead-based immunoassay
 
b. ELISA
 

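### Annex 1 (finding mixed infections) and Annex 2 (true deletion prevalence) promise results that conventional PCR, an assay they allow, cannot give; the optional deletion prevalence would then be biased low, while the 5% decision is not affected by HRP2-positive mixed infections

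*Protocol*

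**What the plan says.** Two separate statements are at issue.

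- **Annex 1** concerns optional extra testing, if funds allow, of a subset of HRP2 RDT-positive samples. It says this will identify infections with *pfhrp2* deleted and *pfhrp3* present, "as well as multiclonal infections with parasites with and without *pfhrp2/3* deletions". Neither the paragraph nor Table A1.1 names or restricts the assay.
- **Annex 2, section 3**, on testing all *P. falciparum*-positive samples, says: "This will enable determination of the true prevalence of *pfhrp2/3* deletions in the sampling domain". Section 1.3 gives full coverage as the condition: "The true prevalence of *pfhrp2/3* deletions can be determined only if all specimens included in the surveys are tested using molecular methods". It explains underestimation only by HRP2/HRP3 cross-reactivity. On the assay, section 3 says: "Different choices of molecular assays and relevant details are provided in the master protocol (section 5.9), and users can follow these guidelines".

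The main text limits what those assays can do.

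- **Section 5.9.2.3** says the conventional method "does not detect gene deletions when *pfhrp2*-deleted parasites are mixed with wild-type parasites in the same sample", and adds that this holds especially when the deleted strain is not predominant. **Table 5** is firmer: "Cannot detect gene deletions when gene-deleted and non-deleted parasites are mixed in the same sample".
- **Section 5.2** makes detection in coinfections depend on techniques such as quantitative PCR, deep sequencing or digital PCR.
- **Section 5.9.2** prefers quantitative PCR but does not require it. **Annex 7, item 17b** lists "a. Conventional PCR" among the methods.
- **Section 5.6** says of moderate to high transmission areas that "the expected higher prevalence of multiclonal infections may mask the presence of *pfhrp2/3*-deleted parasites".

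**The concern.** The annexes state as a plain outcome something that sections 5.2 and 5.9 say depends on the assay. A laboratory that tests every positive sample by conventional PCR meets the only condition in Annex 2, coverage. By the protocol's own account it would still record the gene as present in mixed samples. Optional secondary output 3 (deletion prevalence among all confirmed cases) would then count only infections with no wild-type clone, yet could be reported as true prevalence. A negative result in an Annex 1 subset could be taken to show that no mixed infections exist, when the assay could not have shown them. Because this is a master protocol for many countries and laboratories, figures from different assays may be placed side by side.

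**Working it through.** **Is there a contradiction?** Annex 1 promises detection of mixed infections with any assay. Table 5 says one allowed assay cannot detect the deletion in them. Section 5.9.2.3 agrees, slightly less firmly. Both statements cannot hold for a laboratory using conventional PCR. In Annex 2, coverage does not cure the problem, because a mixed sample that is tested is still read as gene present.

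**Do the annexes carry the condition?** Annex 1 does not. Annex 2, section 1.2, says in general terms that the section 5.2 caveats apply, and points to the assay limitations as Table 4. Table 4 of the protocol is a list of RDT products; the assay table is Table 5. Annex 2, section 4, discusses mixed infections but does not restrict the assay.

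**Direction and size.** The protocol gives no figure to reproduce. Let P be the true prevalence of infections with any deleted clone, s the share of these that are mixed, and d the probability that the assay finds the deletion in a mixed sample:

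reported prevalence = P × (1 − s + s × d)

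Table 5 implies d = 0 for conventional PCR, so the relative bias is −s. P and s are assumptions; d = 0.2 is shown because section 5.9.2.3 is softer than Table 5.

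| s | Reported at P = 10%, d = 0 | Reported at P = 10%, d = 0.2 |
|---|---|---|
| 0 | 10% | 10% |
| 0.1 | 9% | 9.2% |
| 0.3 | 7% | 7.6% |
| 0.5 | 5% | 6% |
| 0.7 | 3% | 4.4% |

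**How s moves with multiclonality.** Assume that a fraction q of clones is deleted, that a share f of infections has two independent clones and the rest one, and that d = 0.

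- Any deleted clone: (1 − f)q + f[1 − (1 − q)²]
- Only deleted clones, all that conventional PCR can call: (1 − f)q + f q²

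At q = 0.10 and f = 0.5, the first is 0.05 + 0.5 × 0.19 = 14.5% and the second is 0.05 + 0.5 × 0.01 = 5.5%.

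| f | Any deleted clone | Found by conventional PCR | Fraction found |
|---|---|---|---|
| 0.2 | 11.8% | 8.2% | 69% |
| 0.5 | 14.5% | 5.5% | 38% |
| 0.8 | 17.2% | 2.8% | 16% |

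For q from 0.05 to 0.20 and f from 0.2 to 0.8, the fraction found runs from 14% (q = 0.05, f = 0.8) to 72% (q = 0.20, f = 0.2).

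**An Annex 1 subset.** Ignore *pfhrp3*, so that only fully deleted infections are HRP2-negative. At q = 0.10 and f = 0.5, the mixed share among HRP2-positive samples is (0.145 − 0.055)/(1 − 0.055) = 9.5%. A subset of 60 (an assumed size) would hold about 5.7 mixed infections, and conventional PCR would find none.

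**The primary result.** In sections 5.6 and 5.10 the numerator of output 1 requires a negative HRP2 RDT. In Annex 2 it requires a negative HRP2 immunoassay. An HRP2-positive mixed infection enters neither numerator, whatever PCR is used.

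**The case against.** The strongest reply is that the protocol already says what is needed. Section 5.2 states the caveat, section 5.9.2 prefers quantitative PCR, section 5.9.2.3 names the methods that find deletions within mixed infections, Annex 2 imports the section 5.2 caveats, and item 17b records the method. The *only if* in Annex 2, section 1.3, can be read as a necessary condition, not a sufficient one. The analyses are optional, and every figure for size is assumed.

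Much of this stands. A reader might infer that Annex 2 ignores the limitation; it does not, because section 1.2 imports it, though loosely and with a wrong table number. But section 3 goes beyond a necessary condition by saying that full testing will enable the true prevalence to be determined. Annex 1 has no caveat at all, and a preference for quantitative PCR does not make the statements true for a laboratory that uses the other method.

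A reader might also infer that any difference between transmission strata would be an artefact of conventional PCR. The documents do not support that. In the model above, a perfect assay would itself report 11.8% and 17.2% for f = 0.2 and f = 0.8 at the same clone frequency. Conventional PCR would report 8.2% and 2.8%, which changes the size and here the order of the difference. Section 5.10 plans breakdowns of outputs 1 and 2, not of output 3. A caution on such comparisons is justified; a ban is not.

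**Conclusion.** The point holds as an inconsistency between two annex statements and sections 5.2 and 5.9. With conventional PCR, optional secondary output 3 and the supplementary results are biased low, in relative terms by the mixed share of deletion-carrying infections (taking Table 5 at its word, d = 0). The direction is certain whenever that share is above zero. The size is not known: the clone frequencies, shares of two-clone infections and independence of clones used here are assumptions.

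A larger relative bias in moderate to high transmission areas fits the expectation in section 5.6. The bias in percentage points also depends on each domain's deletion frequency, which the protocol does not give.

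A reader might infer that the 5% threshold decision is undermined. The documents do not support that, since HRP2-positive mixed infections are outside the numerator of primary output 1. This is a correction worth making to optional analyses, not a flaw in the main result.

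**What to change.** - **Annex 1 (paragraph and Table A1.1) and Annex 2 (sections 1.3 and 3):** make the statements on identifying multiclonal infections and on true prevalence conditional on an assay that resolves mixed infections, namely multiplex real-time PCR or digital PCR (Table 5). Sequencing is better left out here: Table 5 says current approaches are poorly suited to initial deletion identification at lower parasite density, and Table A1.1 says HRP2-positive, Pf-LDH-negative samples may be low density.
- **Where conventional PCR is used:** report the result as a lower bound, the prevalence of infections with no wild-type gene detected. Do not call it true prevalence or take it as evidence that mixed infections are absent.
- **Reporting:** give results by the assay recorded in Annex 7, item 17b, with a caution when comparing across assays or transmission strata.
- **Annex 2, section 1.2:** correct the Table 4 pointer to Table 5.

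The cost is wording, with no added patients, samples or mandatory tests. The downside is that laboratories using conventional PCR can claim less from the optional analysis.
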